9.2.2 Collection of Specimens

Biopsies will be performed at the below timepoints, if tumor is safely accessible for biopsy.

Mandatory:

- Baseline during the Screening Phase or on C1D1 prior to dosing
- After 3-6 weeks of treatment (any time from C2D1-C3D1)

Optional:

- At time of progression

Retreatment

For patients proceeding to the retreatment phase, biopsies will be performed at the below timepoints:

Mandatory:

- At time of progression, prior to restarting sacituzumab govitecan + pembrolizumab (Arm A) or sacituzumab govitecan (Arm B)
- At time of progression on retreatment, if a complete or partial response, or stable disease for \geq 6 months was achieved during the retreatment phase

If dosing is delayed placing the biopsy outside of the allowable window, the biopsy should be rescheduled to be within the window. If not feasible, the biopsy should be obtained as close to within the window as possible. Tissue specimens will be collected from recurrent or metastatic lesions using standard institutional procedures. The amount of tissue collected will follow the guidelines listed below. If a participant has more than one site of disease, only one site needs to be biopsied in order to go on to the study and the site is left to the discretion of the patient and their treating physician. Fine need aspirates (FNA) are not allowed. Participants who undergo a research biopsy procedure for the purpose of this protocol, and in whom inadequate tissue is obtained, are still eligible and are not required to undergo a repeat biopsy in order to enter the study.

- *Breast*: A goal of 3-6 core biopsy specimens will be obtained using standard institutional guidelines for a diagnostic core biopsy of a breast mass.
- *Skin/cheat wall*: A goal of 1-2 4-mm punch biopsies will be obtained.
- *Lymph node*: A goal of 3-6 core biopsy specimens will be obtained using an 18-gauge needle.
- *Liver*: A goal of 3-6 core biopsy specimens will be obtained using an 18-gauge needle.
- *Lung*: Because of the risk of pneumothorax associated with core needle biopsies of lung nodules, no core biopsies of lung nodules will be performed on this protocol, unless they are clinically indicated.
- *Bone*: Because the yield of malignant tissue from bone biopsies tends to be relatively low, no bone biopsies will be performed on this protocol, unless they are clinically indicated.

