- *Pleural fluid:* A goal of 500 cc of pleural fluid will be obtained with a standard thoracentesis procedure, with or without image guidance, according to the clinical judgment of the treating physician and clinician performing the procedure. Less than the goal amount is acceptable and should be based upon the clinical judgment of the Investigator and the clinician performing the procedure. If more than the goal amount of fluid is obtained, then the entire specimen (with the exception of what is needed for clinical purposes, if applicable) will be stored in the tissue bank.
- *Ascites fluid:* A goal of 500 cc of ascites fluid will be obtained with a standard paracentesis procedure, with or without image guidance, according to the clinical judgment of the treating physician and clinician performing the procedure. Less than the goal amount is acceptable and should be based upon the clinical judgment of the Investigator and the clinician performing the procedure. If more than the goal amount of fluid is obtained, then the entire specimen (with the exception of what is needed for clinical purposes, if applicable) will be stored in the tissue bank.

Please note that the above are guidelines for the amount of tissue to be obtained at the baseline biopsy and are not meant to replace clinical judgment at the time the procedure is performed. Less than the goal quantity of tissue is accepted for each type of biopsy and will be left to the clinical judgment of the physician performing the procedure. If ascites or pleural fluid is to be used as the investigational biopsy specimen, consideration should be given to confirming the malignant nature of the ascites or pleural fluid prior to study entry.

If a patient is undergoing resection of a lesion for clinical reasons (i.e. wedge resection of a new lung lesion for confirmation of diagnosis or re-testing of hormone receptor or HER2 status; or, resection of a chest wall lesion; or, resection of a lymph node), then the patient may opt to have a portion of that tissue stored for research at the time of the procedure (provided that the tissue is collected and processed as specified in this section and the Lab Manual), in which case, the participant would not be required to undergo a separate research biopsy for entry into this protocol.

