13.7 Correlative Endpoints

13.7.1 Tumor biopsies and TIL assessment

Previous studies have demonstrated that, in addition to direct cytotoxic effects, chemotherapy-induced cell death can be immunogenic, causing T cell tumor infiltration and sensitizing tumors to immune checkpoint blockade.⁹⁸ Cytotoxic CD8+ T cell infiltration has been reported to increase after treatment with chemotherapy across different tumor types.⁹⁹⁻¹⁰¹ Recently, Herbst et al.

demonstrated that patients who had an increase of at least 5% in expression of PD-L1 in the tumor microenvironment were more likely to respond to the PD-L1 inhibitor atezolizumab.⁵⁸ Modifications in molecular signatures of the tumor microenvironment also correlated with response to therapy.

Tumor-infiltrating lymphocytes (TILs) by histological assessment will be quantitative and evaluated as a percentage of cells stained (0-100%). Data from Loi and colleagues suggest that the mean number of TILs in first-line HR+ / HER2- MBC is likely similar to that observed in first-line metastatic HER2-positive samples from the CLEOPATRA study.¹⁰² The median TIL value was 10% with a mean number of TILs of 17% (standard deviation as a continuous variable of 21%). TILs will be analyzed as a continuous variable using descriptive statistics to summarize the distribution observed among study participants.

A) To assess the relationship between baseline TILs and progression-free survival, we plan to perform a mandatory research biopsy of a safely accessible tumor lesion at baseline. The association of TILs and PFS will be evaluated in a proportional hazards regression model with treatment effect and study stratification factors as covariates.¹⁰³ Linear and non-linear components of the model will be assessed using Wald-type tests. If a non-linear association is detected, the point estimate and 95% prediction bands will be reported for the log relative hazard over the entire distribution of TILs. If no significant non-linear effects are observed, the step-down model will evaluate the linear multivariate proportional hazards regression model and report the adjusted hazard ratio and 95% confidence interval for a linear increase in TILs. In addition, modification of the treatment effect will be explored as an interaction test, and if non-significant (two-sided alpha = 0.05), the step-down model with main effects will be reported.

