B) To assess the absolute change in the percentage of TILs before and after starting treatment, a mandatory biopsy at 3-6 weeks post-treatment (any time between C2D1 and C3D1) is required, if tumor is safely accessible. This on-treatment biopsy will be performed in, at least, the first 27 patients with accessible disease in each arm. Assuming the drop-out/non-evaluable rate will be 10%, 24 paired samples will be available.

Descriptive statistics will be used to summarize the distribution of TILs observed at baseline and after 3-6 weeks of therapy (e.g., mean, standard deviation, median, and inter-quartile range). The evaluation of change in TILs within each arm will be based on a paired t-test (absolute difference) using a one-sided alpha = 0.05 for each arm. Based on the variability of TILs reported by Loi and colleagues in paired specimens before and after treatment with chemotherapy for TNBC, with 24 evaluable paired specimens anticipated per arm and a standard deviation of eight, there will be 82% power to detect an increase in mean TILs from 22.3% to 26.5%, under an assumption of an additive shift model with a Gaussian common density function.

If paired biopsies at baseline and at 3-6 weeks after treatment are obtained in 24 paired samples in each arm (assuming a drop-out/non-evaluable rate of 10% in the entire study population), there will be statistical power to detect the following change in TILs between both study arms. Assuming that the mean difference in TILs from pre-treatment to 3-6 weeks after starting protocol therapy is 10.4% in Arm A (sacituzumab govitecan + pembrolizumab) and 4.2% in Arm B (sacituzumab govitecan alone), with a standard deviation of 8, using a Wilcoxon-Mann-Whitney test with one-

sided alpha of 0.05, the study has 80% power to detect the difference of change in TILs between Arm A (sacituzumab govitecan + pembrolizumab) and Arm B (sacituzumab govitecan alone).

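### The between-arm TIL-change test leaves out baseline TILs that are already measured; the stated power reproduces at SD 8, but 8 is not labelled as the SD of change and biopsy-site mixing is not handled

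*Combined protocol and SAP*

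**What the plan says.** Section 13.7.1 B sets two tests on the absolute change in TIL percentage from baseline to 3-6 weeks.

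- **Within each arm:** a "paired t-test (absolute difference) using a one-sided alpha = 0.05 for each arm". The plan says that "with 24 evaluable paired specimens anticipated per arm and a standard deviation of eight, there will be 82% power". The effect behind that figure is a rise in the mean of 4.2 points, from 22.3% up to 26.5%. The calculation is made "under an assumption of an additive shift model with a Gaussian common density function", and the variability is credited to TILs "in paired specimens before and after treatment with chemotherapy for TNBC".
- **Between arms:** a Wilcoxon-Mann-Whitney test on the change, 10.4 against 4.2 points, SD 8, one-sided 0.05, stated power 80%. No baseline covariate is named, and Section 13.3 has no stratification factors.

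Earlier in 13.7.1 the plan describes a single TIL reading across patients, from first-line HER2-positive samples: median 10%, mean 17%, and "standard deviation as a continuous variable of 21" per cent. It calls the mean likely similar in HR+/HER2- disease.

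On specimens, Section 9.2.2 says of the biopsy needed to enter the study that "the site is left to the discretion of the patient and their treating physician". Lymph node is an accepted site. For effusions, "A goal of 500 cc of pleural fluid will be obtained", and ascites is treated alike. Section 9.3.3 (Assay 1) defines the measure as the stromal TIL percentage on H&E slides. Section 9 makes all blood and tissue biomarker analyses exploratory.

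**The concern.** Three points in 13.7.1 B affect how well the paired biopsies can answer the TIL question.

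1. **Precision.** Every patient in the between-arm comparison has a baseline TIL value, because a change cannot be computed without one. Raw change uses that value with a fixed coefficient of one. A regression on baseline estimates the coefficient and has smaller variance whenever the within-patient correlation is below one.
2. **The SD.** Both tests need the SD of the change. The plan gives 8, points to paired specimens as its source, and leaves the reader to infer what 8 measures. The source is TNBC treated with chemotherapy, so the figure may not carry over.
3. **Specimen comparability.** If the two specimens come from different organs, the organ difference enters the change as noise. If one is fluid, there is no stroma to score.

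What is at stake is interpretation. A null between-arm result could be read as the absence of a 6.2-point effect at 80% power when the power actually achieved was lower, and some of that loss could be recovered at no cost to patients.

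**Working it through.** **Inputs (13.7.1 B):** 24 pairs per arm (27 x 0.9 = 24.3); within-arm effect 26.5 - 22.3 = 4.2; between-arm effect 10.4 - 4.2 = 6.2; SD 8; one-sided 0.05 (z = 1.645). The within-patient correlation r is not in the documents, so it is an assumption shown as a range.

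**Step 1. Reproduce the stated power, taking 8 as the SD of change.**

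- Within arm, normal approximation: Phi(4.2/8 x sqrt(24) - 1.645) = Phi(2.572 - 1.645) = 82.3%. Exact noncentral t, 23 df: 80.2%. Stated: 82%.
- Between arms, Noether formula: P(X > Y) = Phi(6.2/(8 x sqrt 2)) = 0.708; power = Phi(sqrt(12 x 48 x 0.25) x 0.208 - 1.645) = Phi(2.498 - 1.645) = 80.3%. Simulated Wilcoxon: about 82%. Stated: 80%.

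Both reproduce. If 8 were instead the SD at each time point, the SD of change would be 8 x sqrt(2(1 - r)), and exact within-arm power would be 55% at r = 0, 80% at r = 0.5 and 97% at r = 0.75. The label therefore matters.

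**Step 2. Sensitivity to the SD of change, 24 pairs per arm.**

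| SD of change | Within arm (exact t) | Between arms (simulated Wilcoxon) |
|---|---|---|
| 8 | 80% | 82% |
| 10 | 64% | 65% |
| 12 | 51% | 53% |
| 15 | 38% | 39% |

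**Step 3. What baseline adjustment gains between arms.** Let s be the SD at each time point, equal at both.

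- Variance of raw change: 2s²(1 - r).
- Residual variance after regression on baseline: s²(1 - r²).
- Ratio: (1 + r)/2.

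The equivalent SD is 8 x sqrt((1 + r)/2). The simulation holds the SD of change at 8 under the plan's Gaussian model:

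| r | Ratio | Variance saved | Equivalent SD | Power, Wilcoxon on change | Power, linear model with baseline |
|---|---|---|---|---|---|
| 0.5 | 0.75 | 25% | 6.93 | about 82% | about 92% |
| 0.7 | 0.85 | 15% | 7.38 | about 82% | about 88% |
| 0.93 | 0.965 | about 4% | 7.86 | about 82% | about 85% |

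Simulated type I error stayed near 5% for both methods. Part of the gain comes from replacing a rank test by a linear model on Gaussian data: the unadjusted two-sample t-test at SD 8 already has 84.1%. At r = 0.93 that accounts for most of the difference.

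**Step 4. Shape.** A median of 10, mean of 17 and SD of 21 on a 0-100 scale indicate strong right skew, if the cited HER2-positive figures carry over. This is a reason to specify a rank-based counterpart in advance.

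**Step 5. Specimens.** Set side by side, 9.2.2 accepts lymph node, skin, liver, breast and effusion fluid; 9.3.3 scores stromal TILs; and 13.7.1 B pairs the readings without reference to site. No section links the site of the on-treatment biopsy to that of the baseline biopsy. The documents give no rate of site switching and no between-organ TIL difference, so the size of this effect cannot be computed from them.

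**The case against.** The strongest reply is that the plan is sound as written and little depends on it. Much of this stands.

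- **The power is arithmetically correct.** A reader might infer that the SD of 21 contradicts the SD of 8. It does not. The 21 is the spread of one reading across patients; the 8 is tied to paired specimens. They come from different diseases, and only the mean is called likely similar to HR+/HER2- disease. If 21 did apply at both times, the two would agree at r = 1 - 64/(2 x 441) = 0.927. The documents give no correlation by which to call that wrong.
- **Leaving out baseline does not overstate power.** A reader might infer that the 80% is therefore unsupported. Under randomisation the test on change is valid and adjustment can be expected only to help. It has no bearing on the within-arm 82%.
- **24 pairs is a floor.** The plan sets 27 per arm as a minimum, and Section 3.1.5 makes the repeat biopsy mandatory where tumor is safely accessible, among 55 per arm. With an assumed 36 pairs per arm, the same calculations at SD 10 give about 80% within arm and 81% between arms. The true number is unknown, partly because lung and bone are biopsied only if clinically indicated.
- **The site wording concerns study entry.** The discretion sentence in 9.2.2 is about the biopsy needed to go on study, and the tissue amounts are for baseline. The Laboratory Manual, not among the documents, could hold a site rule. Fluid might be absorbed in the 10% non-evaluable allowance.
- **No false increase follows.** A reader might infer that switching organs creates a spurious within-arm rise. Switching in no consistent direction adds noise and lowers power. A spurious rise needs a directional pattern, and the documents give no evidence of one.

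What remains is the unused baseline value, the unlabelled SD, and the absence of a stated rule for mismatched or fluid specimens.

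**Conclusion.** The point holds as a low-cost improvement to an exploratory analysis. The between-arm test is valid, but baseline adjustment would cut its variance by 25%, 15% or about 4% at correlations of 0.5, 0.7 or 0.93, assuming equal variances at the two times. The stated 82% and 80% are right at an SD of change of 8. They fall to about 64% and 65% at SD 10, and to 51% and 53% at SD 12, if only the minimum 24 pairs per arm are available. The documents do not show that the true SD is above 8; they show only that 8 is borrowed and unlabelled.

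The specimen point is qualitative: mismatched organs would plausibly widen the SD, and fluid does not suit a stromal measure. None of this affects the PFS comparison, from which alone the 110 patients were derived (Section 13.2).

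**What to change.** In Section 13.7.1 B:

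1. Compare arms by a linear model of on-treatment TILs on baseline TILs and arm, on the percentage-point scale so that the target stays the absolute change. Specify in advance a rank-based analysis that also adjusts for baseline, because TILs are likely to be right-skewed.
2. Add a sensitivity analysis limited to pairs of solid tissue from the same organ, and state that fluid specimens are non-evaluable for stromal TILs.
3. Label 8 as the assumed SD of the within-patient change, and give power over a range (for example 8, 10, 12 and 15) and for the number of pairs obtained.

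This needs no new procedure and no new patients. The cost is slightly more analysis work, fewer pairs in the sensitivity set and a less favourable power range. Section 13.2.1 says that accrual is complete, so the restated power serves interpretation and not design. If TIL results by arm have already been examined, the added analyses should be reported as post hoc.

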1.4 Correlative/Exploratory Objectives for Enrolled Participants

- 1.4.1 To explore tissue biomarkers of antitumoral immune activity and tumor genomic instability as predictors of response and resistance to sacituzumab govitecan plus pembrolizumab compared to sacituzumab govitecan alone in patients with HR+ / HER2- MBC.
- To characterize baseline Trop-2 expression by histological assessment and correlate with disease response to treatment (PFS, ORR by RECIST 1.1, OS).
 - To assess changes in Trop-2 staining, from baseline to on-treatment and at-progression, and correlate with disease response to treatment (PFS, ORR by RECIST 1.1, OS).

- To characterize tumor-infiltrating lymphocytes (TILs), by histological assessment, at baseline and correlate with disease response to treatment (PFS, ORR by RECIST 1.1, OS).
 - To characterize the expression of markers of immune cell subsets (i.e., CD8 for cytotoxic T cells, CD68 for macrophages), inhibitory checkpoint pathway molecules (i.e., PD-1, PD-L1, TIM3, LAG3), and co-stimulatory pathway molecules (i.e., GITR, OX40) by immunohistochemistry (IHC) and/or immunofluorescence (IF).
 - To explore whether immunosuppressive and/or immune-stimulating immune marker profiles at baseline correlate with disease response to treatment (PFS, ORR by RECIST 1.1, OS).
 - To characterize mutational load and neoantigen burden at baseline and correlate with disease response to treatment (PFS, ORR by RECIST 1.1, and OS).
 - To characterize RNA expression signatures of immune pathway activation and DNA damage repair deficiency at baseline and correlate with disease response to treatment (PFS, ORR by RECIST 1.1, and OS).
 - To explore whether changes in TILs, immunosuppressive and/or immune-stimulating immune marker profiles, mutational load, neoantigen burden, and RNA expression signatures, between paired biopsies from baseline and after 2 cycles of treatment, correlate with disease response to treatment (PFS, ORR by RECIST 1.1, OS).
 - To explore mechanisms of resistance to sacituzumab govitecan plus pembrolizumab compared to sacituzumab govitecan alone in paired biopsies from baseline and at time of progression.
 - To explore whether the number and/or type of mutations identified using a next generation sequencing (NGS) panel is correlated with patient outcomes (PFS, ORR by RECIST 1.1, and OS). This will be performed on DFCI participants only.

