13.5 Analysis of Primary Endpoints

The primary objective is to compare the median PFS achieved with the experimental combination of sacituzumab govitecan plus pembrolizumab versus sacituzumab govitecan alone, and this will be assessed among all patients who initiated protocol therapy according to the randomized treatment assignment.

PFS is defined as the time from study randomization to disease progression, according to RECIST 1.1 or medical judgment, the latter based on established clinical parameters, such as rising tumor markers and physical exam evidence of progression, i.e., worsening chest wall disease, or death due to any cause, whichever occurred first. Patients alive without disease progression are censored at the date of last disease evaluation. Definitive analysis of the efficacy data will be based on the modified intent-to-treat principle where all patients who initiate protocol therapy will be analyzed as randomized.

The Kaplan-Meier estimates will also be calculated separately for patients allocated to each treatment regimen. Multivariable Cox proportional hazards models will be used to estimate treatment efficacy in PFS with adjusting for potential confounders such as age at study entry, stage (locally advanced or metastatic), visceral metastases (yes or no), level of ER expression (1-9% vs. 10% or greater), and rapid recurrence after completion of adjuvant therapy < 6 months (yes or no). Potential interactions between treatment and clinical factors will be explored in the Cox models. Model diagnostics will be performed to check whether the proportionality assumption is valid in those models. Should it fail, appropriate analysis, such as models with time-dependent effects, will be explored. An exploratory subset analysis in the eligible-only population will also be performed, and results of this analysis will be compared with those from the intent-to-treat population in the primary analysis. Any substantial difference will be carefully examined.

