Optional repeat biopsies will be performed at time of progression to explore changes in TILs and other tissue markers. Descriptive statistics will be used to summarize the change in TILs, and inferences on treatment-effects will use non-parametric tests (e.g., Wilcoxon rank sum) with two-sided alpha 0.05. The association of changes in TILs with clinical outcomes of PFS and OS will be exploratory and hypothesis generating in the subset of patients with evaluable repeat biopsies. Analysis plans will consider using Cox models with time-varying covariates to account for the post-baseline assessments.

C) For secondary correlative endpoints to characterize the expression of tumor markers by immunohistochemistry (IHC) and/or immunofluorescence (IF), descriptive statistics and agglomerative hierarchical clustering techniques will be used to summarize the distribution and patterns of profiles observed in baseline samples. Tests of association with clinical outcomes (PFS, OS, ORR) will be exploratory using Cox proportional hazard and logistic regression models, and inferences will use the Benjamini-Hochberg method to control the false discovery rate. Any positive findings will require validation in future studies with independent samples for unbiased estimates of the association with treatment effects and clinical outcomes.

Efficacy endpoints will be analyzed according to Trop-2 expression, which will be evaluated as percent of positive cells, intensity, a composite score, or another method. Analyses of Trop-2 expression are descriptive and exploratory in nature and intended to examine the distribution of Trop-2 expression levels at different biopsy sites and assess associations between Trop-2 expression and efficacy outcomes, such as PFS, OS and ORR, for which separate analyses will be performed according to Trop-2 expression (above and below median) and treatment group.

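### Trop-2 is planned only as separate median-split analyses by treatment group, with no Trop-2-by-arm term, although TILs in the same section are modelled continuously with an interaction test

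*Combined protocol and SAP*

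**What the plan says.** Section 13.7.1 C gives Trop-2 its own paragraph. The score is left open ("percent of positive cells, intensity, a composite score, or another method"), the status is clear ("Analyses of Trop-2 expression are descriptive and exploratory in nature"), and for PFS, OS and ORR the stated form is: "separate analyses will be performed according to Trop-2 expression (above and below median) and treatment group".

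Three other places bear on this:

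- **Section 13.7.1, TILs.** The section says "TILs will be analyzed as a continuous variable using descriptive statistics". Item A then sets out a proportional hazards model for PFS with linear and non-linear TIL components, and adds that "modification of the treatment effect will be explored as an interaction test", at two-sided 0.05.
- **Section 13.7.1 C, general IHC/IF markers.** The preceding paragraph says "Tests of association with clinical outcomes (PFS, OS, ORR) will be exploratory using Cox proportional hazard and logistic regression models", with false-discovery-rate control. It does not say whether Trop-2 is included, how markers are coded, or whether an arm interaction is fitted.
- **Section 13.5.** "Potential interactions between treatment and clinical factors will be explored in the Cox models". The clinical factors listed do not include Trop-2.

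The objective in Section 1.4.1 is to explore tissue biomarkers "as predictors of response and resistance to sacituzumab govitecan plus pembrolizumab compared to sacituzumab govitecan alone", and baseline Trop-2 is the first item under it.

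**The concern.** Two things are lost by the stated form.

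First, cutting a graded score at the sample median treats all patients on one side as alike, which usually wastes information. The cut also depends on the sample. With the scoring method still open, it would not transfer to the independent validation that the same item asks of positive IHC/IF findings.

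Second, the sentence can mean arms compared within each Trop-2 half, or Trop-2 halves compared within each arm. Neither is a test of whether the difference between arms varies with Trop-2, which is the comparative question in Section 1.4.1. A reader shown a significant result in one half and not in the other will be inclined to infer such a difference, and that inference is unsafe.

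What is at stake is the quality of an exploratory biomarker result. The primary and secondary efficacy conclusions are not affected.

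**Working it through.** **Anchor.** The plan gives no power figure for Trop-2. The PFS design that supplies the events (Section 13.2) is hazard ratio 0.65, one-sided alpha 0.1, 80% power, 100 events, with 1:1 allocation (Section 1.1).

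- Events by Schoenfeld: 4 x (1.2816 + 0.8416)^2 / (ln 0.65)^2 = 97.2, so 98. Freedman's formula gives 101.
- Power at 100 events: Phi(0.4308 x sqrt(100)/2 - 1.2816) = Phi(0.872) = 80.8%.

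The plan's figures are reproduced, so the same approximations are used below.

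**Step 1: information kept by a median split.** For a linear effect this is the squared correlation between the marker and its above-median indicator. The shapes are assumptions, because the documents give none for Trop-2.

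| Assumed shape | Kept | Lost |
|---|---|---|
| U-shaped, beta(0.5, 0.5) | 0.81 | 19% |
| Uniform | 0.75 | 25% |
| Normal | 2/pi = 0.64 | 36% |
| Exponential | 0.48 | 52% |
| Lognormal with the TIL mean 17% and SD 21% of Section 13.7.1, effect linear on the raw scale | 0.29 | 71% |

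If the true effect is a step at the median, the loss is near zero. Simulated Cox interaction models (110 patients, 100 events, 250 runs per scenario) gave losses of 39% (normal), 27% (uniform) and 54% (lognormal).

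**Step 2: separate analyses when there is no interaction.** Take a true hazard ratio of 0.65 in both halves, 50 events in each, and one-sided 0.1 per half.

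- Power per half: Phi(0.4308 x sqrt(50)/2 - 1.2816) = Phi(0.2415) = 59.5%.
- Exactly one half significant: 2 x 0.595 x 0.405 = 48%. Simulation also gave 48%.
- Section 13.2.1 says 100 events will not be reached. With 83 events in total the figure is 2 x 0.542 x 0.458 = 49.6%, and with 60 it is 2 x 0.459 x 0.541 = 49.7%. The result does not depend on reaching 100. (83 is what 75% power would imply, and 60 is illustrative. The plan states neither.)

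**Step 3: what an interaction term would deliver.** Assume a true ratio of hazard ratios of 0.5 between halves, all 110 patients evaluable, a normal marker and two-sided 0.05. With four equal cells the standard error of the log ratio is sqrt(16/events). The continuous term's z is the split z divided by sqrt(2/pi).

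| Events | Split z | Power, split | Continuous z | Power, continuous |
|---|---|---|---|---|
| 100 | 0.693/0.400 = 1.73 | 41% | 2.17 | 58% |
| 83 | 0.693/0.439 = 1.58 | 35% | 1.98 | 51% |
| 60 | 0.693/0.516 = 1.34 | 27% | 1.68 | 39% |

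Simulation at 100 events gave 35% and 54%. With the split, 80% power at 100 events needs a ratio of exp(-2.80 x 0.4) = 0.33.

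**The case against.** The strongest reply is that the plan labels this work descriptive and exploratory and attaches no alpha, power or p-value to Trop-2. Reading one significant half as an interaction would then be a misuse by the reader, not something the plan proposes. The general IHC/IF paragraph may also already bring Trop-2 under Cox and logistic models. This stands as a limit on severity. It does not explain why Trop-2 gets a weaker form than TILs, which are also exploratory, and the general paragraph states neither coding nor an interaction.

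Three stronger readings might be inferred, and the documents do not support them:

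- **That a third of the information, or about 40 of 110 patients, is thrown away.** This needs a normal marker and every patient evaluable. The scale is open and may be ordinal. Tissue is not assured: bone-only disease is eligible (3.1.4), biopsy depends on safe access and archival tissue on availability (3.1.5), and bone and lung-nodule biopsies are done only if clinically indicated (9.2.2).
- **That the plan fails to test whether Trop-2 predicts benefit from sacituzumab govitecan.** Both arms receive that drug (5.1), so no analysis in this trial could test it. An interaction term shows only whether Trop-2 modifies the added effect of pembrolizumab. The pooled main effect addresses association with outcome, which is how the Trop-2 item in 1.4.1 and the background in 2.6.1 put the aim.
- **That a spline-by-arm model costs nothing.** If ORR were the 31.5% cited in 2.4.5 and all 110 patients were evaluable, there would be about 35 responders. An assumed 3-df spline with arm and interaction uses 3 + 1 + 3 = 7 parameters, or about 5 responders each.

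**Conclusion.** The point holds in a limited form. The median split with separate analyses is the only form stated specifically for Trop-2, and no Trop-2-by-arm term is specified. That is out of step with the TIL analysis in the same section and with the comparative wording of Section 1.4.1.

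The size of the information loss is an assumption-based illustration: about 36% for a normal marker with a linear effect, about 19% to 71% across the other shapes tried, and near zero for a step at the median. The 48% figure does not depend on the Trop-2 distribution. It does assume that arms are compared within halves, a common hazard ratio of 0.65, 50 events per half and one-sided 0.1 testing, none of which the plan specifies for Trop-2.

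This is a cheap improvement to an exploratory analysis, with no effect on the primary result.

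**What to change.** In Section 13.7.1 C, state that the exploratory Cox (PFS, OS) and logistic (ORR) models already planned for IHC/IF markers apply to Trop-2, with these details:

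- Trop-2 is entered on its full continuous or ordinal score, as a linear term by default. Non-linearity is checked for PFS, as for TILs.
- The models adjust for arm and include a Trop-2-by-arm term, reported as an estimate with its confidence interval and described as modification of the added effect of pembrolizumab.
- The pooled Trop-2 main effect is reported as association with outcome.
- The median split is kept for Kaplan-Meier curves and descriptive tables.

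The cost is a few sentences of SAP text and a little extra analysis. No new samples are needed and the primary analysis does not change. There are two real downsides. The default rests on a linearity assumption. The interaction estimate also stays imprecise: even under the favourable assumptions above, power is 58% against 41% with the split at 100 events, and it falls with fewer events or fewer evaluable patients. With a linear term the logistic model has 3 parameters, or about 35/3 = 12 responders each on the same ORR assumption, which is why linear is the safer default.
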